Study Design	
This post-market study is a prospective, single arm, open label, multicenter trial. Up to 60 subjects with hypertension will be treated with 0.6 mL of dehydrated alcohol as the neurolytic agent per renal artery. The data of the first 5 treated subjects in the study (including renal duplex ultrasound) will be assessed at the 1-month follow-up by the Data Safety Monitoring Board (DSMB). If no safety concern arises, treatment with 0.6 mL of alcohol will continue according to the protocol.
 
Contenting subjects will be assessed for eligibility and baseline data collected. Subjects will attend the study site for the day of procedure. Subjects will be discharged from the study site per the physician's judgment. Subjects must be maintained on his/her baseline anti-hypertensive medications at the same doses through the 6 months follow up visit unless the study subject has symptomatic hypotension requiring anti-hypertensive medication reduction. Planned increases in anti-hypertensive medications must be in alignment with JNC-8 and/or European Hypertension Guidelines and with approval from the sponsor.
 
Follow-up visits will be performed at 7 days, 1 month, 3 months, 6 months and 12 months post-procedure.

Study Geography/ Number of Planned Investigational Sites	Europe: up to 10 sites in Europe.
Number of Groups/ Arms/ Cohorts	1 group
Number of Subjects	Up to 60
Planned Duration of Subject Participation	Up to 12 months
INVESTIGATIONAL PRODUCT	
Product	
Peregrine System™ Infusion Catheter used to deliver a neurolytic agent (such as dehydrated alcohol) to the perivascular area of the renal arteries to ablate the afferent and efferent sympathetic nerves serving the kidneys
 
Dose: 0.6 mL alcohol per treated renal artery.
 
Mode of administration: Direct infusion to the perivascular space, during an endovascular procedure

SUBJECT SELECTION	
Subjects will be enrolled in the study at the time they sign the informed consent form. No study-specific procedures will be performed until after the subject has provided written informed consent.	

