- Per-protocol (PP): The per-protocol analysis set consists of all subjects treated with the study dose (0.6 mL dehydrated alcohol) and with no major protocol deviations. If any subjects meet these criteria for removal from the full analysis set, then all endpoint analyses will be additionally conducted in this subset of subjects. These analyses will be considered supplementary

All analyses will be conducted using the FAS unless otherwise specified. The FAS will be the primary analysis set for all statistical analyses

Primary Safety Endpoint

The primary safety endpoint is defined as the absence of any of the following events as adjudicated by the Clinical Events Committee (CEC) through 1-month post procedure:

1. Peri-procedural major vascular complications
2. Major Bleeding as defined by the TIMI Bleeding Classification
3. Acute Kidney Injury (AKI) within 1 month of the procedure
4. Peri-procedural death (within 1 month of the procedure)

Primary Performance Endpoint

The primary performance endpoint is defined as any reduction of 24-hour mean ambulatory systolic blood pressure following treatment at 6 months, as compared to baseline.

Secondary Safety Endpoints

Secondary safety endpoints include:

1. Proportion of subjects with a decline in estimated glomerular filtration rate (eGFR) by >25% from baseline to 6-month follow-up;
2. Change in serum creatinine from baseline to 6-month follow-up
3. New renal arterial stenosis > 60% from the baseline at the 6-month follow-up, to be confirmed by the same imaging method used at baseline.
4. Stroke or transient ischemic attack (TIA) within 1 month of the procedure
5. Myocardial Infarction (MI) within 1 month of the procedure
6. Major Adverse Events (MAEs) through 6-month post-procedure.

Adverse events will be recorded at each of the follow-up periods. Severity, device relatedness, and sequelae of each adverse event will be recorded.

Secondary Performance Endpoints

Secondary performance endpoints include the following:

1. Changes in antihypertensive medications at 7 days, 1-, 3-, 6- and 12-months post-procedure
2. Changes in systolic and diastolic clinic/office blood pressure following treatment compared to baseline, assessed at 7 days, 1-, 3-, 6- and 12-months post-procedure

3. Changes in systolic and diastolic 24-hour mean daytime and nighttime ambulatory blood pressure, assessed at 1-, 3-, 6- and 12-months post-procedure

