4. Changes in systolic 24-hour mean ambulatory blood pressure assessed at 1-, 3- and 12-months post-procedure
5. Changes in diastolic 24-hour mean ambulatory blood pressure assessed at 1-, 3-, 6- and 12-months post-procedure
6. Change in eGFR from baseline, to evaluate the progression of Chronic Kidney Disease (CKD) after 1, 3, 6 and 12 months
7. The progression of kidney disease in subjects with ≤ 60 mL/min/1.73m² will be evaluated by comparing the change in eGFR during the study to the historical loss (reduction) of eGFR during the 3 years prior to renal denervation for each individual subject
8. Change in albuminuria from baseline to 3 months post-procedure, with additional assessments at each study time point
9. Change in albuminuria categorization from baseline to 3 months post-procedure, with additional assessments at each study time point
10. Change in serum creatinine and cystatin-C from baseline to 3 months post-procedure, with additional assessments at each study time point

General Considerations

- Continuous variables will be summarized using standard quantitative statistics: number of non-missing observations, mean, standard deviation, median, quartiles and range (minimum and maximum observed values). The number of missing observations, if any, will also be summarized. Categorical variables will be summarized using classical frequency statistics: number of non-missing observations and percentages by categories. Number and percent of missing data, if any, will also be summarized.
- For all success/failure endpoints (including but not limited to primary safety endpoint), the 95% 2-sided exact binomial confidence intervals will be presented.
- Demographics, medical history and procedural characteristics will be summarized as noted above.
- For each variable, the baseline value will be defined as the last value collected before the procedure.
- There will be no formal hypothesis testing conducted in the study. Ninety-five percent confidence intervals, when presented, are intended to be descriptive in nature only. For binary variables, confidence intervals will be calculated via exact binomial methods. For continuous variables, the confidence interval of the mean will be constructed using the normal approximation.

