- Unless otherwise noted, only complete data will be reported and no imputation for missing values will be conducted. Sensitivity analyses will be conducted for the primary safety and efficacy endpoints whereby missing data will be imputed using multiple imputation and LOCF methods.

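### The renal artery stenosis rate (SAP secondary safety item 3) is read only at 6 months, so a stenosis documented earlier and then treated, or followed by death or drop-out, leaves that rate.

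*SAP*

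**What the plan says.** The SAP's Secondary Safety Endpoints list gives item 3 as "New renal arterial stenosis > 60% from the baseline at the 6-month follow-up, to be confirmed by the same imaging method used at baseline". Item 6 of the same list is worded differently: "Major Adverse Events (MAEs) through 6-month post-procedure". Items 4 and 5 (stroke or TIA, and myocardial infarction) also count events over a window, in their case one month.

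The last bullet of General Considerations sets the missing-data rule: "Unless otherwise noted, only complete data will be reported and no imputation for missing values will be conducted". The exception follows it: "Sensitivity analyses will be conducted for the primary safety and efficacy endpoints whereby missing data will be imputed using multiple imputation and LOCF methods". Item 3 is neither of those endpoints.

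The plan does collect information before month 6. The Protocol Summary schedules visits at 7 days, 1 month and 3 months, and says under Study Design: "The data of the first 5 treated subjects in the study (including renal duplex ultrasound) will be assessed at the 1-month follow-up". The SAP has adverse events recorded at every follow-up. Nothing in the supplied text says how item 3 treats a stenosis found and treated before month 6, or a subject who has a documented stenosis and then dies or leaves.

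**The concern.** A safety endpoint read at one visit describes the subjects who reach that visit, in the state they are in on that day. Stenosis is a harm that can be corrected once it is found, so its absence at month 6 does not show that it never occurred. Two routes take a documented event out of item 3:

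- **Found, treated, still in the study.** The 6-month image shows an open artery, so there is no stenosis to count at that visit.
- **Found, then death or drop-out.** There is no 6-month image, and the complete-data rule removes the subject from both numerator and denominator.

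The procedure delivers a neurolytic agent around the renal artery, so new stenosis is a direct organ-specific safety question. The SAP's sample-size section says the results are meant to help plan a larger study. A reader of that later plan would take item 3 as the rate of new stenosis over six months, which it is not.

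**Working it through.** **Inputs.** Up to 60 treated subjects (Protocol Summary). 10% assumed to lack the 6-month performance evaluation, leaving 60 × 0.9 = 54 (SAP, Sample Size Calculation). Exact binomial 95% intervals (SAP, General Considerations). Applying the 54 to the 6-month artery image is my assumption, because the SAP states the attrition for the performance endpoint. The numbers of early events are also assumed, since the documents give no stenosis rate.

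**Formula.** Clopper-Pearson limits for x events in n subjects: lower = Beta(0.025; x, n − x + 1), upper = Beta(0.975; x + 1, n − x). For x = 0 the upper limit is 1 − 0.025^(1/n).

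**The SAP's own figures first.**

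- n = 60: 51/60 gives a width of 19.48% and 60/60 gives 5.96% (stated 19.5% and 6.0%).
- n = 54: 46/54 gives 20.50% and 54/54 gives 6.60% (stated 20.5% and 6.6%).

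All four reproduce. They do not bear on the stenosis rate itself, but they confirm the interval method and that the SAP expects about 6 of 60 subjects without 6-month performance data.

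**Route 1: treated and still followed.** Assume all 60 are imaged at month 6 and no stenosis is present then.

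| Early treated stenoses | Item 3 as written | Any time through month 6 |
|---|---|---|
| 1 | 0/60 = 0% (0 to 6.0%) | 1/60 = 1.7% (0.04 to 8.9%) |
| 2 | 0/60 = 0% (0 to 6.0%) | 2/60 = 3.3% (0.4 to 11.5%) |

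One such subject moves the upper limit by 8.94 − 5.96 = 2.98 points. Two move it by 11.53 − 5.96 = 5.57 points.

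**Route 2: documented, then lost.** Assume 54 are imaged at month 6 with no stenosis, and k of the 6 leavers had a documented stenosis. Item 3 as written reads 0/54 = 0% (0 to 6.6%) whatever k is. Over all 60, with leavers who have no known event taken as event-free, k = 1 gives 1/60 = 1.7% (0.04 to 8.9%), k = 2 gives 2/60 = 3.3% (0.4 to 11.5%) and k = 3 gives 3/60 = 5.0% (1.0 to 13.9%).

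**Direction.** Complete-case analysis also removes event-free leavers, and that pushes the other way. One stenosis present at month 6 with six event-free leavers reads 1/54 = 1.9%, against 1/60 = 1.7% over all treated subjects. The net effect on the rate depends on who leaves. What is certain is that documented early events leave the numerator.

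**The case against.** The strongest reply is that little is lost from the study as a whole. Adverse events are recorded at each follow-up with severity, device relatedness and sequelae. MAEs run through 6 months. Major vascular complications and AKI sit in the adjudicated 1-month primary endpoint. Numbers missing are to be reported, and no hypothesis is tested. This stands, and it limits the importance of the point. It does not repair item 3. The supplied text, which is a summary, does not list the MAE components, so nobody can check from it whether item 6 would capture a treated stenosis. The item 3 rate would omit it either way.

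A second reply is that early stenosis may seldom be found. The only artery imaging that the supplied text names after the procedure and before month 6 is the 1-month duplex in the first 5 subjects. A reader might infer that the plan also calls for unscheduled imaging when blood pressure or renal function worsens, but the supplied text does not say so. An early case would come from that duplex or from an adverse event report. This stands too, and it is why the size is given only as an illustration.

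A third reply concerns confirmation. Item 3 requires the baseline imaging method, and the exclusion criteria name MRA/CTA and/or renal angiography for screening. Counting any early duplex signal would loosen the definition. That is right, and the fix keeps the requirement.

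A reader might also extend the criticism to item 1, "Proportion of subjects with a decline in estimated glomerular filtration rate (eGFR) by >25% from baseline to 6-month follow-up". The documents do not support treating that as an error. A fixed 6-month reading is a legitimate landmark for sustained decline, while an any-visit rule would also count transient dips. The earlier values are already summarised: "Change in eGFR from baseline, to evaluate the progression of Chronic Kidney Disease (CKD) after 1, 3, 6 and 12 months".

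**Conclusion.** The point holds for item 3. As worded, and with no rule to the contrary in the supplied text, a stenosis documented and treated before month 6 is scored as no event, and one followed by death or drop-out is dropped. The second consequence follows directly from the complete-data rule. The first is an inference from the wording.

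In illustration, one or two such subjects among 60 change 0% (0 to 6.0%) to 1.7% (0.04 to 8.9%) or 3.3% (0.4 to 11.5%). These figures rest on assumed event counts and, for leavers, on no undetected stenosis.

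Two stronger conclusions should not be drawn. The first is that the reported rate can only be too low: event-free leavers are dropped as well, so the direction is not fixed. The second is that early events vanish from the safety report: they may appear among adverse events or MAEs. This is a cheap improvement to a descriptive secondary endpoint.

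**What to change.** - **Definition.** Make item 3 new renal artery stenosis > 60% documented at any time from procedure through the 6-month follow-up, including any renal artery revascularisation for new stenosis in that period.
- **Confirmation.** Keep confirmation by the baseline imaging method where it was done. Report separately any early event that was treated or lost before such confirmation.
- **Landmark.** Keep the 6-month rate as its own line.
- **Denominator.** Report the cumulative rate over all treated subjects (the FAS). Show how many lack a 6-month image, and state the rule for leavers without a known event. Add a complete-case version. Do not bring back only those leavers who had an event, because the denominator would then be chosen by outcome and the rate inflated.
- **Optional.** Tabulate a > 25% eGFR decline at any scheduled visit through 6 months as a supplement to item 1, which stays a 6-month landmark.

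The cost is SAP wording and one extra tabulation from data already collected. The reported rate may be slightly less favourable, and if leavers without a known event are counted as event-free, it assumes that none had an undetected stenosis.

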STATISTICAL ANALYSIS PLAN SUMMARY

TITLE: A Post-Market Study of Transcatheter Perivascular Renal Denervation for the Treatment of Hypertension using the Ablative Solutions Inc. Peregrine System™ Infusion Catheter

SHORT TITLE: The Peregrine Post-Market Study

PROTOCOL ID: CR0001

INVESTIGATIONAL PRODUCT: Peregrine System™ Infusion Catheter

INDICATION: Hypertension

ClinicalTrials.gov ID: NCT02570113

PHASE: Post market clinical follow up study

SPONSOR: Ablative Solutions, Inc.
[name]

COORDINATING INVESTIGATORS: [name]. med. [name]

SAP VERSION: Final 2.0

DATE: 28 October 2018

*

ENDPOINTS AND STATISTICAL ANALYSIS**Sample Size Calculation**

The study is not powered for formal hypothesis testing.

The primary safety endpoint is defined by the absence of any of the following events as adjudicated by the CEC through 1-month post procedure:

1. Peri-procedural major vascular complications
2. Major Bleeding as defined by the thrombolysis in myocardial infarction (TIMI) Bleeding Classification
3. Acute Kidney Injury (AKI) within 1 month of the procedure
4. Peri-procedural death (within 1 month of the procedure)

With a sample size of 60 evaluable subjects for the primary safety endpoint which is expected to vary between 85% and 100%, the associated width of the 95% 2-sided exact binomial confidence intervals range from 19.5% to 6.0%, respectively. This accuracy was deemed satisfactory and sufficient to fulfill the study objectives and to provide relevant information to design appropriately a larger study.

The primary performance endpoint is defined as a reduction of 24-hour mean ambulatory systolic blood pressure following treatment at 6 months, as compared to baseline. Assuming 10% of subjects will not participate in the performance evaluation at 6-months (death, drop-out, loss-to-follow-up, withdrawal), then with a sample size of 54 evaluable subjects and results on primary performance endpoint expected to vary between 85% and 100%, the associated width of the 95% 2-sided exact binomial confidence intervals range from 20.5% to 6.6%, respectively. This accuracy was deemed satisfactory and sufficient to fulfill the study objectives and to provide relevant information to design appropriately a larger study.

Endpoints and Planned Statistical Analysis

The following populations are defined for analysis:

- Full Analysis Set (FAS): The full analysis set contains all consented and treated subjects

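### The SAP's normal-approximation rule makes confidence intervals for means slightly too narrow (about 94.5% coverage at 54 to 60 subjects); a t interval corrects or clarifies this at almost no cost

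*SAP*

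**What the plan says.** The rule is in the SAP, General Considerations: "For continuous variables, the confidence interval of the mean will be constructed using the normal approximation". The sentence just before it sets a different standard for proportions: "For binary variables, confidence intervals will be calculated via exact binomial methods". The same bullet limits the role of all such intervals: "There will be no formal hypothesis testing conducted in the study" and "Ninety-five percent confidence intervals, when presented, are intended to be descriptive in nature only".

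The SAP's Sample Size Calculation gives the planned numbers: 60 evaluable subjects for the primary safety endpoint and, after 10% loss by 6 months, a performance evaluation "with a sample size of 54 evaluable subjects". The protocol summary gives 60 as an upper limit on enrolment.

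The SAP gives no SD for any continuous endpoint and does not say whether the multiplier is z or t. It states no other interval method for means. Any interval shown for a mean change in office or ambulatory blood pressure, eGFR, serum creatinine or cystatin-C would therefore follow this rule.

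**The concern.** When the SD is estimated from the sample, the standardised mean of normal data follows a t distribution with n − 1 degrees of freedom, not a normal distribution. A multiplier of 1.960 is then a little too small. The error always goes the same way: the interval claims slightly more precision than the data support, and the gap grows as n falls.

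The plan already uses exact methods for proportions. For means, the t interval is exact under normality and just as easy to program, so there is little reason to specify the approximation. The wording also leaves room for two programmers to produce different limits, one using z and the other t.

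Little is at stake. No test, decision rule or sample size rests on these intervals, and the reported means, SDs, medians and quartiles do not change. The interest is only that an interval labelled 95% should have that coverage for normal data, and that the instruction should be unambiguous.

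**Working it through.** **Inputs**
- n = 60 and n = 54: SAP, Sample Size Calculation. The second follows from the first: 60 × (1 − 0.10) = 54.
- Level 95%, two-sided, z = 1.960: the plain reading of General Considerations.
- Normal data with the SD estimated from the sample: an assumption, since the documents give neither an SD nor a distribution.

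**The plan's own figures.** The SAP states no width or coverage for intervals of means. The widths it does give are exact binomial, and all four reproduce with Clopper-Pearson limits:

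| Successes / n | Recomputed width | SAP |
|---|---|---|
| 51/60 (85%) | 19.48% | 19.5% |
| 60/60 (100%) | 5.96% | 6.0% |
| 46/54 (nearest count to 85%) | 20.50% | 20.5% |
| 54/54 (100%) | 6.60% | 6.6% |

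The sample size rationale is therefore sound on this point and is not affected by what follows.

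**Coverage of the z interval.** For normal data, coverage = 2 × T(1.960) − 1, where T is the t distribution function with n − 1 degrees of freedom.
- n = 54 (53 df): 0.9447, a shortfall of 0.9500 − 0.9447 = 0.0053.
- n = 60 (59 df): 0.9453, a shortfall of 0.9500 − 0.9453 = 0.0047.

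A simulation with normal data (200,000 replicates at each size) agrees: z covers 94.5% at n = 54 and 94.6% at n = 60, and t covers 95.0% at both.

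**Width.** The ratio of t to z width is t(0.975, n − 1) / 1.960, and the half-width in SD units is the multiplier divided by √n.

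| n | t multiplier | Ratio to 1.960 | Half-width, z | Half-width, t | Difference |
|---|---|---|---|---|---|
| 54 | 2.0057 | 1.023 | 0.2667 SD | 0.2729 SD | 0.0062 SD |
| 60 | 2.0010 | 1.021 | 0.2530 SD | 0.2583 SD | 0.0053 SD |

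**In mmHg.** The documents give no SD for the change in blood pressure. If it lay between 10 and 20 mmHg (an assumption), the t interval would add to each half-width:
- n = 54: 0.0062 × 10 = 0.06 mmHg to 0.0062 × 20 = 0.12 mmHg.
- n = 60: 0.0053 × 10 = 0.05 mmHg to 0.0053 × 20 = 0.11 mmHg.

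**Smaller groups.** The same coverage formula gives 94.3% at n = 40, 94.03% at n = 30 and 93.998% at n = 29, so the shortfall exceeds one percentage point only below 30 subjects. The documents do not establish that any group given an interval is that small. The per-protocol set is analysed only if subjects are removed from the full set, and of its analyses the SAP says "These analyses will be considered supplementary". Secondary performance endpoint 7, on subjects with eGFR of 60 or below, promises no interval for a mean. Purely as illustration, coverage would be 93.5% at n = 20 and 91.8% at n = 10.

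**The case against.** The strongest reply is that this is a preference and not an error. A normal-approximation interval for a mean is a standard large-sample method, 54 to 60 subjects is a reasonable size for it, and the SAP openly calls it an approximation. The intervals are descriptive, and a change of about 0.1 mmHg in a limit would alter no reader's interpretation. All of that stands, and it fixes the point as minor. It does not show that z is preferable to t.

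Second, the SAP does not say 1.96. The phrase could mean an interval resting on approximate normality of the mean, as opposed to a bootstrap or rank-based one, and a programmer could implement that with t. This also stands, and it makes the shortfall conditional on the plain reading. Under the other reading the sentence is ambiguous, and the same edit resolves it.

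Third, the contrast with exact binomial methods is imperfect. Exact binomial intervals hold at least their nominal level whatever the true proportion, whereas t is exact only for normal data. For strongly skewed variables t does little: in a simulation with an assumed lognormal (log-SD 1, n = 54), coverage was 89.6% with z and 90.2% with t. This limits the claim to roughly normal data, and albuminuria may not qualify. Most of the listed endpoints are changes from baseline, for which skewness may be less of a problem than for levels.

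Last, revising a final SAP carries some administrative cost. That is true but small.

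**Conclusion.** The point holds and is minor. On the plain reading, nominal 95% intervals for means cover 94.47% at n = 54 and 94.53% at n = 60, about half a percentage point short, and t intervals would be 2.3% and 2.1% wider. This assumes a multiplier of 1.960, an SD estimated from the sample, roughly normal data and the planned numbers of evaluable subjects. If fewer subjects are evaluable, the gap widens slowly.

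The normal approximation is not invalid at this size. The t interval is simply better for normal data at every n, and the present wording leaves the multiplier open. The exact binomial intervals and the sample size rationale are untouched.

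**What to change.** In the SAP, General Considerations, replace the sentence on intervals for continuous variables with: *Confidence intervals for means of continuous variables will use the t distribution with n − 1 degrees of freedom.*

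This changes one sentence and needs no new data, extra analysis or change in sample size. The intervals become about 2% wider at the planned size. Because the SAP is marked final, the change would ordinarily be recorded as a revision or a documented note. If t was already intended, only the wording changes.

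### The missing-data sensitivity analyses for the primary endpoints give no lower bound, and as written LOCF can count a subject who died as a 6-month performance success

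*SAP*

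**What the plan says.** SAP, General Considerations, sets the default: "Unless otherwise noted, only complete data will be reported and no imputation for missing values will be conducted". It then adds: "Sensitivity analyses will be conducted for the primary safety and efficacy endpoints whereby missing data will be imputed using multiple imputation and LOCF methods". The SAP names no other missing-data analysis for the primary endpoints. The per-protocol analysis is a supplementary subset, not a bound on missing data.

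The endpoints are both scored yes or no:

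- Safety (SAP, Primary Safety Endpoint): "absence of any of the following events as adjudicated by the Clinical Events Committee (CEC) through 1-month post procedure".
- Performance (SAP, Primary Performance Endpoint): "any reduction of 24-hour mean ambulatory systolic blood pressure following treatment at 6 months, as compared to baseline".

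SAP, Sample Size Calculation, plans 60 evaluable subjects for safety and gives no figure for 1-month loss. For performance it plans 54, and it lists death among the reasons for loss: "Assuming 10% of subjects will not participate in the performance evaluation at 6-months (death, drop-out, loss-to-follow-up, withdrawal". Ambulatory pressure is also measured before 6 months (SAP, Secondary Performance Endpoints): "Changes in systolic 24-hour mean ambulatory blood pressure assessed at 1-, 3- and 12-months post-procedure". The Protocol Summary, Study Design, places a 7-day visit before the 1-month visit.

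There is no hypothesis test, and the intervals are declared descriptive. The SAP does say that their precision should help to design a larger study.

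**The concern.** A sensitivity analysis is useful if it can move the result in the direction that would worry a reader. For an endpoint defined by the absence of events, carrying the last status forward cannot do that. A subject with a recorded event is already a failure, so a subject missing at 1 month is normally one with no recorded event, and LOCF turns that subject into a success. Multiple imputation that assumes missing subjects resemble observed ones stays close to the complete-case result when few events are seen.

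For performance, no rule in the visible text says how a death is scored. The 1- and 3-month readings give LOCF something to carry past a death, so a subject who was not alive at 6 months can enter the numerator of a 6-month endpoint.

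At stake is how the intervals are read. If they are to inform a larger study, the planned tables may suggest robustness to missing data that has not been tested downwards.

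**Working it through.** **Method.** Clopper-Pearson 95% limits for x successes in n: the lower limit is the 0.025 quantile of Beta(x, n−x+1), and the upper limit is the 0.975 quantile of Beta(x+1, n−x). When x = n, the lower limit is 0.025^(1/n) and the upper is 100%.

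**The SAP's own figures reproduce.** For safety the SAP states "the associated width of the 95% 2-sided exact binomial confidence intervals range from 19.5% to 6.0%, respectively". 51/60 gives 73.4 to 92.9 (width 19.5), and 60/60 gives 94.0 to 100 (6.0). For performance it states "the associated width of the 95% 2-sided exact binomial confidence intervals range from 20.5% to 6.6%, respectively". 46/54 gives 72.9 to 93.4 (20.5), and 54/54 gives 93.4 to 100 (6.6). These widths are not in dispute.

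**Performance, at the SAP's assumed loss of 10% (6 of 60)**

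| Observed | Handling | Rate | 95% CI | Width |
|---|---|---|---|---|
| 46 of 54 | Complete-case, 46/54 | 85.2% | 72.9–93.4 | 20.5 |
| 46 of 54 | LOCF, all 6 carried as reductions, 52/60 | 86.7% | 75.4–94.1 | 18.7 |
| 46 of 54 | Missing as not met, 46/60 | 76.7% | 64.0–86.6 | 22.7 |
| 54 of 54 | Complete-case, 54/54 | 100% | 93.4–100 | 6.6 |
| 54 of 54 | Missing as not met, 54/60 | 90.0% | 79.5–96.2 | 16.7 |

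If k of the 6 carried values show a reduction, LOCF gives (46+k)/60, from 46/60 to 52/60. This assumes that every missing subject has a value to carry; otherwise the denominator could lie between 54 and 60. LOCF equals the lower bound only if all 6 are carried and none shows a reduction. With k = 5 it gives 51/60 = 85.0%, just below complete-case, so it exceeds complete-case here only when k = 6.

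Multiple imputation without covariates (an assumption) would score about 6 × 46/54 = 5.1 of the 6 as successes, close to complete-case.

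One death after a reduction, added to the 54 observed: 47/55 = 85.5% if LOCF scores it a success, and 46/55 = 83.6% if it is scored as not met.

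**Safety, with assumed missing counts (the SAP gives none)**

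| Assumed case | Complete-case | LOCF | Missing as event |
|---|---|---|---|
| No events, 1 missing | 59/59, lower limit 93.9% | 60/60, lower limit 94.0% | 59/60 = 98.3% (91.1–99.96) |
| No events, 3 missing | 57/57, lower limit 93.7% | 60/60, lower limit 94.0% | 57/60 = 95.0% (86.1–99.0) |
| No events, 6 missing | 54/54, lower limit 93.4% | 60/60, lower limit 94.0% | 54/60 = 90.0% (79.5–96.2) |
| 9 events, 3 missing | 48/57 = 84.2% (72.1–92.5) | 51/60 = 85.0% (73.4–92.9) | 48/60 = 80.0% (67.7–89.2) |

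**Multiple imputation for safety, no observed events.** With n observed, m missing, a uniform prior on the event rate and no covariates (assumed), the chance that one imputed dataset contains any failure is 1 − (n+1)/(n+m+1). For m = 3 it is 1 − 58/61 = 4.9%; for m = 6 it is 1 − 55/61 = 9.8%. A Jeffreys prior gives 2.5% and 5.1%. At 85% success with 3 missing it is 1 − 0.85³ = 39%, so the statement that imputation adds few failures holds only when events are rare.

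**The case against.** The strongest case against has five parts.

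- **Inference.** The SAP does not say how LOCF is applied to an adjudicated binary composite, and the document is headed as a summary. Rules for LOCF and deaths may exist in fuller text. This stands as a caveat: the safety reading is an inference from what is visible. Nor does the SAP say how a reported but unadjudicated event is counted.
- **Size.** LOCF's upward shift from complete-case is small: 0.3 points in the safety lower limit with no events and 3 missing, 0.8 points in the safety rate with 9 events and 3 missing, at most 1.5 points for performance, and 0.3 points for a single death. This stands.
- **The bound is extreme.** Missing-as-event supposes that every subject lost by 1 month had an event, although two of the four components arise around the procedure and there is a 7-day visit. Agreed; it is a bound, not an estimate of bias.
- **Recoverable.** The SAP summarises the number missing, so a reader could work out the bound. True, but planning it ahead fixes how deaths count before the data are seen.
- **Nothing is decided on it.** There is no test or threshold. With no events, the missing-as-event safety widths (8.9, 12.9 and 16.7 points for 1, 3 and 6 missing) stay within the SAP's accepted 6.0 to 19.5. At the 85% ends the excess is about 2 points: 21.5 against 19.5 for safety with 3 missing, and 22.7 against 20.5 for performance.

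A reader might infer that LOCF biases the primary result, or that it always flatters performance. The documents support neither. The main analysis is complete-case, LOCF is only a sensitivity analysis, and for performance it can lower the rate as well as raise it.

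**Conclusion.** The concern holds as a gap in the sensitivity analyses, not as an error in the main result or in the stated precision. For safety, as the visible SAP reads, LOCF can only confirm or raise the complete-case rate, and multiple imputation with no departure adjustment adds little when events are rare. For performance, LOCF as written can count a subject who died after a 1- or 3-month reduction as a 6-month success. That needs a death after the 1-month reading and before 6 months, with the last value below baseline; if the last value was not below baseline, the same rule scores a failure.

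The unreported distance to the bound is larger than LOCF's own upward effect. For performance at the SAP's 10% loss, the rate falls by 8.5 points (85.2% to 76.7%) at the lower end of the expected range and by 10 points (100% to 90.0%) at the upper end. For safety with no events, the lower limit falls to 91.1%, 86.1% or 79.5% with 1, 3 or 6 missing. The safety counts and the imputation priors are assumptions. In a descriptive study this is worth changing because it is cheap.

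**What to change.** Amend the missing-data paragraph in SAP, General Considerations:

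1. **Safety.** Add an analysis that counts every subject without 1-month status as having had an event, labelled as the worst-case bound. Drop LOCF for this endpoint, or keep it labelled as the best case.
2. **Performance.** Do not carry ambulatory pressure forward after death. Add an analysis that counts death or a missing 6-month reading as endpoint not met. Keep multiple imputation.

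The cost is SAP wording and a few extra tables, with no new data collection. The downside is a possibly less favourable lower limit in the report.
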